13.1.2.3 Expedited Reporting and Investigator Safety Letters

Vertex, as study sponsor, is responsible for reporting suspected, unexpected, serious adverse reactions (SUSARs) involving the study drug(s) to all regulatory authorities, IECs, and participating investigators in accordance with ICH Guidelines and/or local regulatory requirements, as applicable. In addition, Vertex, or authorized designee, will be responsible for the submission of safety letters to central IECs.

It is the responsibility of the investigator or designee to promptly notify the local IRB/IEC of all unexpected serious adverse drug reactions involving risk to human subjects.

13.2 Administrative Requirements

13.2.1 Ethical Considerations

The study will be conducted in accordance with the current ICH GCP Guidelines, which are consistent with the ethical principles founded in the Declaration of Helsinki, and in accordance with local applicable laws and regulations. The IRB/IEC will review all appropriate study documentation to safeguard the rights, safety, and well-being of the subjects. The study will be conducted only at sites where IRB/IEC approval has been obtained. The protocol, Investigator's Brochure, sample ICF, advertisements (if applicable), written information given to the subjects (including diary cards), safety updates, annual progress reports, and any revisions to these documents will be provided to the IRB/IEC by the investigator or Vertex, as allowable by local applicable laws and regulations.

13.2.2 Subject Information and Informed Consent

After the study has been fully explained, written informed consent will be obtained from the subject before study participation. The method of obtaining and documenting the informed consent and assent (if applicable) and the contents of the consent will comply with ICH GCP and all applicable laws and regulations and will be subject to approval by Vertex or its designee.

13.2.3 Investigator Compliance

No modifications to the protocol will be made without the approval of both the investigator and Vertex. Changes that significantly affect the safety of the subjects, the scope of the investigation, or the scientific quality of the study (i.e., efficacy assessments) will require IRB/IEC notification before implementation, except where the modification is necessary to eliminate an apparent immediate hazard to human subjects. Vertex will submit all protocol modifications to the required regulatory authorities.

When circumstances require an immediate departure from procedures set forth in the protocol, the investigator will contact Vertex to discuss the planned course of action. If possible, contact will be made before the implementation of any changes. Any departures from the protocol will be fully documented in the source documentation and in a protocol deviation log.

13.2.4 Access to Records

The investigator will make the office and/or hospital records of subjects enrolled in this study available for inspection by Vertex or its representative at the time of each monitoring visit and for audits. The records will also be available for direct inspection, verification, and copying, as required by applicable laws and regulations, by officials of the regulatory health authorities (FDA and others). The investigator will comply with applicable privacy and security laws for use and disclosure of information related to the research set forth in this protocol.

13.2.5 Subject Privacy

To maintain subject confidentiality and to comply with applicable data protection and privacy laws and regulations, all CRFs, study reports, and communications relating to the study will identify subjects by assigned subject numbers, and access to subject names linked to such numbers will be limited to the site and the study physician and will not be disclosed to Vertex.

As required by applicable laws and regulations in the countries in which the study is being conducted, the investigator will allow Vertex and/or its representatives access to all pertinent medical records to allow for the verification of data gathered in the CRFs/SAE Forms and the review of the data collection process. The FDA and regulatory authorities in other jurisdictions, including the IRB/IEC, may also request access to all study records, including source documentation, for inspection.

For sites participating in the US, and in accordance with the Health Insurance Portability and Accountability Act (HIPAA) and associated regulations, an executed HIPAA authorization will be obtained by the site from each subject (or the legal representative of the subject) before research activities may begin. Each HIPAA authorization will comply with all HIPAA requirements including authorization allowing the site access to and use of the subject's personally identifiable health information, authorization for the site to disclose such information to Vertex, the FDA, and other parties requiring access under the protocol, and statements as to the purpose for which such information may be used and for how long.

13.2.6 Record Retention

The investigator will maintain all study records according to ICH GCP Guidelines and/or applicable local regulatory requirement(s), whichever is longest, as described in the Clinical Trial Agreement. If the investigator withdraws from the responsibility of keeping the study records, custody will be transferred to a person willing to accept the responsibility and Vertex will be notified.

13.2.7 Study Termination

At any time, Vertex may terminate this study in its entirety or may terminate this study at any particular site. In addition, for reasonable cause, either the investigators or their IRBs/IECs may terminate the study at their center.

Conditions that may lead to reasonable cause and warrant termination include, but are not limited to:

- Subject or investigator noncompliance
- Unsatisfactory subject enrollment
- Lack of adherence to protocol procedures
- Lack of evaluable and/or complete data
- Potentially unacceptable risk to study subjects
- Decision to modify drug development plan
- Decision by the FDA or other regulatory authority

Written notification that includes the reason for the clinical study termination is required.

13.2.8 End of Study

The end of study is defined as the last scheduled visit (or contact) of the last subject.

13.3 Data Quality Assurance

Vertex or its designated representative will conduct a study site visit to verify the qualifications of each investigator, inspect clinical study site facilities, and inform the investigator of responsibilities and procedures for ensuring adequate and correct study documentation.

The investigator is required to prepare and maintain adequate and accurate case histories designed to record all observations and other data pertinent to the study for each subject. Study data for each enrolled subject will be entered into a CRF by study site personnel using a secure, validated, web-based electronic data capture (EDC) application. Vertex will have read-only access to site-entered clinical data in the EDC application.

Instances of missing, discrepant, or uninterpretable data will be queried with the investigator for resolution. Any changes to study data will be made to the CRF and documented in an audit trail, which will be maintained within the clinical database.

13.4 Monitoring

Monitoring and auditing procedures developed or approved by Vertex will be followed to comply with GCP Guidelines. On-site checking of the CRFs/SAE Forms for completeness and clarity, cross-checking with source documents, and clarification of administrative matters will be performed.

The study will be monitored by Vertex or its designee. Monitoring will be done by personal visits from a representative of Vertex or designee (study site monitor), who will review the CRFs/SAE Forms and source documents. The study site monitor will ensure that the investigation is conducted according to the protocol design and regulatory requirements.

13.5 Electronic Data Capture

Vertex will provide the study sites with secure access to and training on the EDC application sufficient to permit study site personnel to enter or correct information in the CRFs on the subjects for which they are responsible.

A CRF will be completed for each enrolled study subject. It is the investigator's responsibility to ensure the accuracy, completeness, clarity, and timeliness of the data reported in the subject's CRF. Source documentation supporting the CRF data will indicate the subject's participation in the study and will document the dates and details of study procedures, AEs, other observations, and subject status.

[figure not shown]
The investigator, or designated representative, will complete the CRF as soon as possible after information is collected.

The audit trail entry will show the user's identification information and the date and time of any correction. The investigator will provide formal approval of all the information in the CRFs, including any changes made to them, to endorse the final submitted data for the subjects for whom the investigator is responsible.

Vertex will retain the CRF data and corresponding audit trails. A copy of the final archival CRF in the form of a compact disc (CD) or other electronic media will be placed in the investigator's study file.

13.6 Publications and Clinical Study Report

13.6.2 Clinical Study Report

A CSR, written in accordance with the ICH E3 Guideline, will be submitted in accordance with local regulations.

APPENDIX A Eligible MF *CFTR* Mutations

“MF” mutations are a subset of minimal function mutations that are non-responsive to TEZ, IVA, or TEZ/IVA. A mutation is considered an MF mutation if it meets at least 1 of the following 2 criteria:

- (1) biological plausibility of no translated protein (genetic sequence predicts the complete absence of *CFTR* protein), or
- (2) in vitro testing that supports lack of responsiveness to TEZ, IVA, or TEZ/IVA, and evidence of clinical severity on a population basis (as reported in large patient registries).

Inclusion of MF Mutations Based on In Vitro Testing

Mutations that were considered to be MF mutations based on in vitro testing met the following criteria in in vitro experiments:

- baseline chloride transport that was <10% of wild-type *CFTR*
- an increase in chloride transport of <10% over baseline following the addition of TEZ, IVA, or TEZ/IVA in the assay

These mutations also had evidence of clinical severity on a population basis (per *CFTR2* patient registry; accessed on 15 May 2018). Patients with these mutations on one allele and *F508del* on the other allele exhibited evidence of clinical severity as defined as:

- average sweat chloride >86 mmol/L, and
- prevalence of pancreatic insufficiency (PI) >50%

These clinical severity criteria do not apply to the individual subjects to be enrolled in the study, but were used to categorize each mutation on a population level.

Eligible MF Mutations

The list below represents acceptable mutations, which are detectable by an FDA-cleared genotyping assay or other method (e.g., sequencing); however, this list may not include every eligible mutation, and investigators should contact the medical monitor regarding other mutations that may also meet study eligibility criteria.

CFTR Mutations Eligible for VX18-121-101 (Parts 1

MF Mutation Category	Mutation				
Nonsense mutations	Q2X	L218X	Q525X	R792X	E1104X
	S4X	Q220X	G542X	E822X	W1145X
	W19X	Y275X	G550X	W882X	R1158X
	G27X	C276X	Q552X	W846X	R1162X
	Q39X	Q290X	R553X	Y849X	S1196X
	W57X	G330X	E585X	R851X	W1204X
	E60X	W401X	G673X	Q890X	L1254X
	R75X	Q414X	Q685X	S912X	S1255X
	L88X	S434X	R709X	Y913X	W1282X
	E92X	S466X	K710X	Q1042X	Q1313X
	Q98X	S489X	Q715X	W1089X	Q1330X
	Y122X	Q493X	L732X	Y1092X	E1371X
	E193X	W496X	R764X	W1098X	Q1382X
	W216X	C524X	R785X	R1102X	Q1411X
	Canonical splice mutations	185+1G→T	711+5G→A	1717-8G→A	2622+1G→A
296+1G→A		712-1G→T	1717-1G→A	2790-1G→C	3500-2A→G
296+1G→T		1248+1G→A	1811+1G→C	3040G→C	3600+2insT
405+1G→A		1249-1G→A	1811+1.6kbA→G	(G970R)	3850-1G→A
405+3A→C		1341+1G→A	1811+1643G→T	3120G→A	4005+1G→A
406-1G→A		1525-2A→G	1812-1G→A	3120+1G→A	4374+1G→T
621+1G→T		1525-1G→A	1898+1G→A	3121-2A→G	
711+1G→T			1898+1G→C		
Small (≤3 nucleotide) insertion/deletion (ins/del) frameshift mutations	182delT	1078delT	1677delTA	2711delT	3737delA
	306insA	1119delA	1782delA	2732insA	3791delC
	306delTAGA	1138insG	1824delA	2869insG	3821delT
	365-366insT	1154insTC	1833delT	2896insAG	3876delA
	394delTT	1161delC	2043delG	2942insT	3878delG
	442delA	1213delT	2143delT	2957delT	3905insT
	444delA	1259insA	2183AA→G ^a	3007delG	4016insT
	457TAT→G	1288insTA	2184delA	3028delA	4021dupT
	541delC	1343delG	2184insA	3171delC	4022insT
	574delA	1471delA	2307insA	3171insC	4040delA
	663delT	1497delGG	2347delG	3271delGG	4279insA
	849delG	1548delG	2585delT	3349insT	4326delTC
	935delA	1609del CA	2594delGT	3659delC	
Non-small (>3 nucleotide) insertion/deletion (ins/del) frameshift mutations	CFTRdele1	CFTRdele16-17b	1461ins4		
	CFTRdele2	CFTRdele17a,17b	1924del7		
	CFTRdele2,3	CFTRdele17a-18	2055del9→A		
	CFTRdele2-4	CFTRdele19	2105-2117del13insAGAAA		
	CFTRdele3-10,14b-16	CFTRdele19-21	2372del8		
	CFTRdele4-7	CFTRdele21	2721del11		
	CFTRdele4-11	CFTRdele22-24	2991del32		
	CFTR50kdel	CFTRdele22,23	3667ins4		
	CFTRdup6b-10	124del23bp	4010del4		
	CFTRdele11	602del14	4209TGTT→AA		
	CFTRdele13,14a	852del22			
	CFTRdele14b-17b	991del5			

CFTR Mutations Eligible for VX18-121-101 (Parts 1

MF Mutation Category	Mutation			
Missense mutations that	A46D ^b	V520F	Y569D ^b	N1303K
• Are not responsive in vitro to TEZ, IVA, or TEZ/IVA	G85E	A559T ^b	L1065P	
	R347P	R560T	R1066C	
and	L467P ^b	R560S	L1077P ^b	
• %PI >50% and SwCl ⁻ >86 mmol/L	I507del	A561E	M1101K	

CFTR: cystic fibrosis transmembrane conductance regulator; IVA: ivacaftor; SwCl: sweat chloride; TEZ: tezacaftor
 Source: CFTR2.org [Internet]. Baltimore (MD): Clinical and functional translation of CFTR. The Clinical and Functional Translation of CFTR (CFTR2), US Cystic Fibrosis Foundation, Johns Hopkins University, the Hospital for Sick Children. Available at: <http://www.cftr2.org/>. Accessed 15 May 2018.

Notes: %PI: percentage of *F508del-CFTR* heterozygous patients in the CFTR2 patient registry who are pancreatic insufficient; SwCl: mean sweat chloride of *F508del-CFTR* heterozygous patients in the CFTR2 patient registry.

^a Also known as 2183delAA→G.

[figure not shown]
^b Unpublished data.

### **3 INTRODUCTION**

This statistical analysis plan (SAP) for the final data analysis is based on the most recently approved clinical study protocol (CSP), electronic case report form (eCRF), and eCRF completion guidelines.

This is a Phase 2, randomized, double-blind, placebo- and TEZ/IVA-controlled, parallel group, multicenter study to evaluate the safety and efficacy of VX-121 in triple combination with TEZ/VX-561 and in triple combination with TEZ/IVA in subjects aged 18 years and older with cystic fibrosis.

This SAP (Methods) documents the planned final statistical analyses of efficacy endpoints and safety endpoints defined in the study protocol for VX18-121-101.

The Vertex Biometrics Department will perform the statistical analysis described in this document. SAS (Version 9.4 or higher) will be used to generate all statistical outputs (tables, figures, listings, and datasets).

The SAP (Methods) will be finalized and approved prior to the completion of Parts 1 and 2. Any revisions to the approved SAP will be documented and approved in an amendment to the SAP prior to the completion of Parts 1 and 2. Any changes made to the SAP Methods after the completion of Parts 1 and 2 will be documented in the clinical study report for this study.

### **4 STUDY OBJECTIVES**

#### **4.1 Primary Objective**

**Parts 1 (Subjects with F/MF genotypes) and 2 (Optional; Subjects with the F/F genotype)**

- To evaluate the safety and tolerability of VX-121 in TC with TEZ/VX-561 (deuterated IVA)
- To evaluate the efficacy of VX-121 in TC with TEZ/VX-561

#### **4.2 Secondary Objectives**

**Parts 1 and 2**

- To evaluate the pharmacodynamic (PD) effect of VX-121 in TC with TEZ/VX-561
- To evaluate the pharmacokinetics (PK) of VX-121 when administered in TC with TEZ/VX-561
- To evaluate the PK of TEZ, VX-561, and their respective metabolites when administered in TC with VX-121

## **5 STUDY ENDPOINTS**

### **5.1 Primary Endpoint**

- Safety and tolerability, based on the assessment of adverse events (AEs), laboratory test results, standard 12-lead ECGs, vital signs, and spirometry
- Absolute change from baseline in percent predicted forced expiratory volume in 1 second (ppFEV1) through Day 29

### **5.2 Secondary Endpoints**

- Absolute change from baseline in sweat chloride concentrations through Day 29
  - Absolute change from baseline in Cystic Fibrosis Questionnaire-Revised (CFQ-R) respiratory domain score at Day 29
  - PK parameters of VX-121, TEZ, VX-561, [REDACTED] and relevant metabolites
- [REDACTED]

## **6 STUDY DESIGN**

### **6.1 Overall Design**

This is a Phase 2, [REDACTED] proof-of-concept study of VX-121. A schematic of the study design for Part 1 is shown in [Figure 6-1](#), which has a randomized, double-blind, placebo-controlled, parallel-group design and evaluates VX-121 in TC with TEZ/VX-561.

**Figure 6-1 VX18-121-101 Study Design for Part 1 (F/MF Genotypes)**

	Treatment Period a,b (4 weeks)	Washout Period b (18 ± 3 days)	
Screening Period (4 weeks)	TC-20 mg (VX-121/TEZ/VX-561) N = 18	TEZ/ VX-561	Safety Follow-up Period (4 weeks)
	TC-10 mg (VX-121/TEZ/VX-561) N = 18		
	TC-5 mg (VX-121/TEZ/VX-561) N = 9		
	Triple Pbo N = 9	Dual Pbo	

F/MF: *F508del*/minimal function; N: number of subjects; Pbo: placebo; ppFEV1: percent predicted forced expiratory volume in 1 second; qd: daily; TC: triple combination; TEZ: tezacaftor

Note: Randomization will be stratified by ppFEV1.

a The planned VX-121 doses are 5 mg, 10 mg, and 20 mg qd.

b The dosage of TEZ and VX-561 will be TEZ 100 mg qd and VX-561 150 mg qd.

A schematic of the study design for Part 2 is shown in [Figure 6-2](#), which has a randomized, double-blind, TEZ/IVA-controlled, parallel-group design and evaluates VX-121 in TC with TEZ/VX-561.

**Figure 6-2 VX18-121-101 Study Design for Part 2 (F/F Genotype)**

	Run-in Period a,b (4 weeks)	Treatment Period b,c (4 weeks)	Washout Period b (4 weeks)	
Screening Period (4 weeks)	TEZ/IVA	TC-20 mg (VX-121/TEZ/VX-561) N = 18	TEZ/IVA	Safety Follow-up Period (4 weeks)
		Pbo + TEZ/IVA N = 9		

FDC: fixed-dose combination; F/F: *F508del/F508del*; IVA: ivacaftor; N: number of subjects; Pbo: placebo; ppFEV1: percent predicted forced expiratory volume in 1 second; q12h: every 12 hours; qd: daily; TC: triple combination; TEZ: tezacaftor

Note: Randomization will be stratified by ppFEV1.

a All subjects are required to complete the TEZ/IVA Run-in Period to establish a reliable on-treatment (TEZ/IVA) baseline.

b The dosage of TEZ/IVA will be TEZ 100 mg qd/IVA 150 mg q12h, which will be administered as TEZ 100 mg/IVA 150 mg FDC in the morning and IVA 150 mg in the evening.

c Part 2 will evaluate the same VX-121 dose (20 mg qd) used in Part 1. The dosage of TEZ and VX-561 will be TEZ 100 mg qd and VX-561 150 mg qd.

## 6.2 Sample Size and Power

The primary objectives of Parts 1, 2, [REDACTED] are the evaluation of safety, tolerability, and efficacy of VX-121 in TC with TEZ/VX-561 [REDACTED] in subjects with CF. The sample size calculations described below are deemed adequate to evaluate the primary objectives, based on clinical and statistical considerations.

### Safety and Tolerability

The primary safety endpoints are safety and tolerability. Approximately 108 subjects with CF will be enrolled in the study with approximately 81 subjects receiving VX-121 in TC with either TEZ/VX-561 [REDACTED]. In case only Parts 1 and 2 are conducted, approximately 63 subjects will receive VX-121 in TC with TEZ/VX-561. The sample size for each treatment group will provide sufficient data for a descriptive analysis of AEs.

### Efficacy

The primary efficacy endpoint is the absolute change from baseline in ppFEV1 through Day 29. A sample size of 18 subjects per treatment group provides at least 90% power to detect a mean within-treatment change of 7 percentage points. These calculations assumed a standard deviation of 8 percentage points for the absolute change from baseline in ppFEV1 and were based on EAST, Version 6.4.1.

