9 STUDY IMPLEMENTATION

9.1 Study Design

This is a Phase 2, [REDACTED] proof-of-concept study of VX-121. Study parts may be conducted in parallel or sequentially.

A schematic of the study design for Part 1 is shown in Figure 9-1, which has a randomized, double-blind, placebo-controlled, parallel-group design and evaluates VX-121 in TC with TEZ/VX-561.

Figure 9-1 VX18-121-101 Study Design for Part 1 (F/MF Genotypes)

	Treatment Period ^{a,b} (4 weeks)	Washout Period ^{b,c} (18 ± 3 days)	
Screening Period (4 weeks)	TC-20 mg (VX-121/TEZ/VX-561) N = 18	TEZ/ VX-561	Safety Follow-up Period (4 weeks)
	TC-10 mg (VX-121/TEZ/VX-561) N = 18		
	TC-5 mg ^d (VX-121/TEZ/VX-561) N = 9		
	Triple Pbo N = 9		
		Dual Pbo	

FDC: fixed-dose combination; F/MF: *F508del*/minimal function; N: number of subjects; pbo: placebo; PD: pharmacodynamic; PK: pharmacokinetic; ppFEV₁: percent predicted forced expiratory volume in 1 second; qd: daily; TC: triple combination; TEZ: tezacaftor

Note: Randomization will be stratified by ppFEV₁.

- ^a The planned VX-121 doses of 5 mg, 10 mg, and 20 mg qd may be adjusted based on emerging data from subjects with CF in Part D of Study VX17-121-001 (Study 001). However, no more than 3 dose levels of VX-121 will be evaluated, and the highest dose will not exceed 20 mg qd.
- ^b The dosage of TEZ and VX-561 will be TEZ 100 mg qd and VX-561 150 mg qd.
- ^c The Washout Period (18 ± 3 days) is included to enable a more thorough evaluation of VX-121 exposure-response relationships by conducting PK and PD assessments during the VX-121 washout.
- ^d TC-5 mg is optional.

A schematic of the study design for Part 2 is shown in Figure 9-2, which has a randomized, double-blind, TEZ/IVA-controlled, parallel-group design and evaluates VX-121 in TC with TEZ/VX-561. Part 2 is an optional part of the study, which will be conducted at the sponsor’s discretion.

Figure 9-2 VX18-121-101 Study Design for Part 2 (F/F Genotype)

	Run-in Period ^{a,b} (4 weeks)	Treatment Period ^{b,c} (4 weeks)	Washout Period ^{b,d} (4 weeks)	
Screening Period (4 weeks)	TEZ/IVA	TC-20 mg (VX-121/TEZ/VX-561) N = 18	TEZ/IVA	Safety Follow-up Period (4 weeks)
		Pbo + TEZ/IVA N = 9		

FDC: fixed-dose combination; F/F: *F508del/F508del*; IVA: ivacaftor; N: number of subjects; pbo: placebo; PD: pharmacodynamic; ppFEV₁: percent predicted forced expiratory volume in 1 second; q12h: every 12 hours; qd: daily; TC: triple combination; TEZ: tezacaftor

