12.3.4 Efficacy Analysis

12.3.4.1 Spirometry

The absolute change from baseline for ppFEV₁ through Day 29 is a primary endpoint in Parts 1, 2, [REDACTED]. The within-group comparisons in the absolute change from baseline for ppFEV₁ through Day 29 will be the primary analysis. A mixed-effects model for repeated measures (MMRM) with change from baseline for ppFEV₁ at Days 15 and 29 as the dependent variable will be performed for the FAS for each part. The null within-group hypothesis of no difference in the mean absolute change from baseline through Day 29 for ppFEV₁, in all treatment groups, by part, will be tested. The model will include treatment group, visit, and treatment-by-visit interaction as fixed effects, subject as random effect and the continuous baseline ppFEV₁ as a covariate. The model will be estimated using restricted maximum likelihood. Denominator degrees of freedom for the *F* test for fixed effects will be estimated using the Kenward-Roger approximation. A compound symmetry covariance structure will be used to model the within-subject errors. Conditional on the fixed effects, missing data due to treatment or study discontinuation will be assumed to be missing at random.

Adjusted means and 95% CIs of the average treatment effects through Day 29 (averaged over Days 15 and 29), as applicable, will be estimated within MMRM using least squares (LS) means via PROC MIXED in SAS, for all within-group comparisons in all parts. *P* values will also be provided for these comparisons. In addition, adjusted means and 95% CIs for the absolute change from baseline for ppFEV₁ through Day 29 will be estimated for between-group comparisons.

For endpoints other than primary, no multiplicity adjustments will be made and the corresponding *P* values for these endpoints will be considered as nominal.

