##### **8.3.1.2 Primary Analysis for Parts 1, 2, [REDACTED]**

The null hypothesis to be tested is that the mean absolute within-group change from baseline in ppFEV1 through Day 29 is zero for VX-121 in triple combination (TC) with TEZ/VX-561 in Parts 1 and 2, [REDACTED] separately. A 2-sided *p*-value of 0.05 or less will be interpreted as sufficient evidence to reject the null hypothesis.

The primary analysis will be performed using a mixed-effects model for repeated measures (MMRM) with change from baseline in ppFEV1 at Day 15 and Day 29 as the dependent variable for each part, separately. The model will include treatment group, visit, and treatment-by-visit interaction as fixed effects and subject as a random effect, with the continuous baseline ppFEV1 as a covariate. For Part 1 the model will include 4 treatment groups: placebo, TC-5 mg, TC-10 mg, TC-20 mg. For Part 2, the model will include 2 treatment groups: placebo + TEZ/IVA, and TC-20 mg. [REDACTED]

[REDACTED] The model will be estimated using restricted maximum likelihood. Denominator degrees of freedom for the F test for fixed effects will be estimated using the Kenward-Roger approximation. An unstructured covariance structure will be used to model the within-subject errors. If the model estimation does not converge, a compound symmetry covariance structure will be used instead.

Conditional on the observed data and covariates, missing ppFEV1 data will be assumed to be missing at random; consequently, no imputation of missing data will be performed.

The adjusted means and 95% confidence intervals (CI) of the average treatment effect through Day 29 (average over Day 15 and Day 29 only) will be presented for all within-treatment and between-treatment comparisons, for each part. A 2-sided *p*-value will be provided for within-treatment comparisons.

Further, the adjusted mean and corresponding 95% CI for each treatment group and the treatment difference between each triple combination and placebo or TEZ/IVA at Day 15 and Day 29 will be provided, for each part. A 2-sided p-value will be provided for within-treatment comparisons.

The adjusted mean (with SE) obtained from the MMRM analysis at Day 15 and Day 29 will be plotted by treatment group, for each part.

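### Does the 90% power statement leave the optional nine-subject TC-5 mg arm wrongly covered?

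*SAP*

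**What the plan says.** SAP 6.2 (Efficacy) states: "A sample size of 18 subjects per treatment group provides at least 90% power to detect a mean within-treatment change of 7 percentage points". The next sentence gives an SD of 8 points for the absolute change from baseline in ppFEV₁. Protocol 12.1 and the synopsis carry the same statement. SAP 6.2 opens with a general judgement: "The sample size calculations described below are deemed adequate to evaluate the primary objectives, based on clinical and statistical considerations".

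The design figures show unequal arms. In Part 1, TC-20 mg and TC-10 mg have 18 subjects each, and SAP Figure 6-1 lists "TC-5 mg (VX-121/TEZ/VX-561) N = 9", with nine more on placebo. A footnote to Protocol Figure 9-1 adds "TC-5 mg is optional"; SAP Figure 6-1 has no such note. In Part 2, TC-20 mg has 18 subjects and the TEZ/IVA control has nine. The SAP's headcount includes the 5 mg arm: "In case only Parts 1 and 2 are conducted, approximately 63 subjects will receive VX-121 in TC with TEZ/VX-561", which is 18 + 18 + 9 + 18.

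On analysis, SAP 8.3.1.2 says "For Part 1 the model will include 4 treatment groups: placebo, TC-5 mg, TC-10 mg, TC-20 mg". Its null hypothesis of zero within-group change covers VX-121 in triple combination without excepting a dose, and a two-sided p-value "of 0.05 or less will be interpreted as sufficient evidence to reject the null hypothesis". Protocol 12.3.4.1 puts it more broadly: the within-group null "in all treatment groups, by part, will be tested". SAP 8.1 applies no multiplicity adjustment, so each test is at 5%.

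**The concern.** The power sentence is phrased per treatment group, is the only one of its kind, and sits under a statement that the calculations are adequate for the primary objectives. One of the three planned VX-121 arms in Part 1 has half the subjects that the sentence assumes, yet it enters the same primary model and is judged by the same 0.05 criterion. Neither document gives a power for it or labels its test descriptive.

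A hurried reader could carry the 90% over to TC-5 mg. What would be at stake is interpretation. If TC-5 mg missed 0.05 while the two larger arms reached it, the pattern might be taken as evidence about dose when it could come from sample size alone. That matters somewhat here, because Protocol 9.3.2 wants the dose levels to inform exposure-response analyses of efficacy.

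**Working it through.** **Inputs.** Mean change 7, SD 8, n = 18 (SAP 6.2); two-sided alpha 0.05 (SAP 8.3.1.2; the power sentence itself does not state alpha); n = 9 for TC-5 mg (SAP Figure 6-1).

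**Formula.** Power from the noncentral t distribution with noncentrality (7/8)·√n and critical value t(0.975, df). Two choices of df:

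- df = n − 1, a stand-alone one-sample t test.
- df = 49, an assumed proxy for the Part 1 MMRM with pooled variance: 54 subjects − 4 group means − 1 baseline covariate.

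**The plan's own figure, n = 18.** Noncentrality = 0.875 × 4.243 = 3.712.

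- df 17, critical value 2.110: power 93.8%.
- df 49, critical value 2.010: power 95.3%.

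The stated minimum of 90% is reproduced. On df = n − 1 it holds down to n = 16 (90.5%).

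**The same inputs at n = 9.** Noncentrality = 0.875 × 3 = 2.625.

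- df 8, critical value 2.306: power 63.5%.
- df 49, critical value 2.010: power 73.0%.
- Normal approximation: 74.7%.

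With a true 7-point change the arm would miss 0.05 in about 27% (df 49) to 37% (df 8) of trials, against about 5% to 6% for an arm of 18.

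**Detectable change and precision.** The half-width is t(0.975, df) × 8/√n, with 8/√9 = 2.667 and 8/√18 = 1.886.

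| n | df | Change detectable at 90% power | 95% CI half-width |
|---|---|---|---|
| 9 | 8 | 9.9 | 6.1 |
| 9 | 49 | 8.8 | 5.4 |
| 18 | 17 | 6.5 | 4.0 |
| 18 | 49 | 6.2 | 3.8 |

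**Sensitivity to the meaning of the SD.** The documents do not say whether 8 is the SD of a single-visit change or of the Day 15/Day 29 average. If single-visit, the SD of the average is 8·√((1 + ρ)/2), where ρ is an assumed between-visit correlation.

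| ρ | SD of average | Power at n = 9, df 8 | Power at n = 9, df 49 |
|---|---|---|---|
| 0.9 | 7.80 | 65.6% | 75.2% |
| 0.7 | 7.38 | 70.4% | 79.7% |
| 0.5 | 6.93 | 75.7% | 84.4% |

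No two-sided reading reaches 90% at n = 9.

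**What the text commits to.** The arithmetic shows that 90% does not apply to nine subjects. Whether the plan claims that it does is a matter of wording. The power sentence names its sample size, 18. The figure giving nine for TC-5 mg comes just before SAP 6.2. The adequacy sentence rests on clinical as well as statistical considerations and promises no power for each arm. SAP 8.3.1.2 says what a p-value of 0.05 or less means; it attaches no conclusion to a larger one, and no passage ties a dose decision to the TC-5 mg p-value.

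**The case for a change.** The strongest case for a change is that being optional decides whether the arm is run, not how it is tested. Once run, it falls under a primary hypothesis, and the only adequacy argument in the plan does not reach it. One limiting sentence in SAP 6.2 would add no subjects and no analyses, and it would warn readers in advance not to take a miss at the lowest dose as absence of effect.

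Much of this stands. The arm is inside the primary model, it has no stated power, and its power is materially lower under every reading of the inputs. What does not follow is that the plan needs correcting. The warning restates how any non-significant result from nine subjects should be read, and the adjusted mean and 95% interval that show the imprecision are already planned for every group. The figures to insert would themselves rest on an assumed 49 degrees of freedom, an assumed meaning of the SD, and a 7-point effect at 5 mg for which the documents give no dose-specific basis. Changing the same statement in the protocol would also count as a protocol modification under Protocol 13.2.3, with approvals and regulatory submission, for a sentence that is already true.

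**Conclusion.** No change is needed. The power statement is correct for the groups it describes (93.8% at n = 18) and makes no claim about nine subjects. For TC-5 mg the power to detect a 7-point change is about 63% to 75% if SD 8 applies to the Day 15/29 average, and up to about 84% if 8 is a single-visit SD with correlation 0.5. These figures assume full enrolment, no dropout, and a true 7-point change at 5 mg.

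This is an unstated figure, not an arithmetic error or a promise that the design fails to keep. A smaller, optional low-dose arm is a fair trade-off in a proof-of-concept study that also uses its doses for exposure-response work. Stating the figure would leave the model, the estimates, the type I error and the actual power as they are. When results are reported, TC-5 mg should be read from its adjusted mean and interval, whose half-width is roughly 5 to 6 points against about 4 for an arm of 18. The planned outputs already allow that.
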